6.3 Clinical Event Committee (Safety Committee)

An independent clinical events committee (safety committee) (CEC) will be utilized in this study for adverse event adjudication. All clinical events will be reviewed by the committee. The committee will consist of three physicians who are not participating in the clinical study. The physicians will either be heart failure or interventional specialists. A charter will be developed governing the working of the committee. A chairperson will be designated to run the committee meetings and to work with the committee to ratify the CEC charter prior to any event review. CEC meetings will be scheduled based on the number of events or on trial milestones, but no less than twice a year while the study is ongoing. The last CEC meeting will occur after all subjects have been enrolled and have completed the protocol required follow up period and when all adverse event forms and source documentation have been received by the sponsor.

The sponsor will ensure that adequate source documentation is gathered prior to bring an event before a committee. Additionally, the sponsor will remove all identifiers to site and patient. If an event goes to the CEC and the committee requests additional source documentation, the event will be listed as pending and every attempt will be made to bring the event back to the next meeting.

Reports will show the CEC classification, once final as the final classification. In interim reports, pending events will be listed with the investigator classification. Deaths will be reported separately and the event leading to the death will be shown separately only if designated by the CEC as a separate event. Example, death from cardiac arrest is not reported as both a cardiac arrest and a cardiac arrest death.

7. Statistical Considerations

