1 INTRODUCTION

This statistical analysis plan (SAP) describes the statistical methods and data handling methods to be followed during final reporting and any interim analyses of data collected for the study Protocol PVP017.

This SAP should be read in conjunction with the study protocol and case report form (CRF). This version of the plan has been developed using the protocol Rev G, CRF dated Jan 12, 2022, and Medication Memo dated Mar 9, 2022.

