7.8 Main Study Endpoints

7.8.1 Primary Safety

A Primary Safety analysis will be performed for the As-Treated population to include:

- Percentage of patients with Serious Adverse Events (SAE) defined as the total number of patients with a CEC-classified SAE from the time of enrollment through 30 days post-implant Follow-Up, compared to the total number of patients within the population. Patients with two or more CEC-classified SAE will be counted only once.
- Percentage of patients with Serious Procedure Related Adverse Events (SPRAE) defined as the total number of patients with CEC-classified SPRAE from the time of implant procedure through 30 days post-implant Follow-Up, compared to the total number of patients within the population. Patients with two or more CEC-classified SPRAE will be counted only once. Procedure Related Adverse Events will be defined as any AE related to Aortix Pump Deployment Procedure or Aortix Pump Retrieval Procedure.

Descriptive summaries will be provided for both Percentage of patients with SAE and Percentage of patients with SPRAE for As-Treated population. Corresponding listing will be provided for As-Treated Population.

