7.12 Deaths

The number of patients who died during the study will be provided along with a vignette discussing the primary cause of death, the temporal course of death and classification for As-Treated population by subgroup and overall.

Only CEC classification of Deaths will be used for analysis.

Listing with detailed information will be provided for the ITT population.

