7.13 Interim Analysis

Interim analysis(es) will be conducted in this trial. An interim analysis once 15 patients have been enrolled and/or implanted will be performed. Other ad hoc analyses may be requested.

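### Interim primary safety rates can be biased low: the SAP counts only CEC-classified events and sets no adjudication or 30-day follow-up condition for the interim

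*SAP*

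**What the plan says.** SAP section 1 describes its methods as those "to be followed during final reporting and any interim analyses of data collected", so its definitions apply at the interim unless it says otherwise.

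- **SAE rate (SAP 7.8.1).** The numerator is the "total number of patients with a CEC-classified SAE from the time of enrollment". The denominator is every As-Treated patient, and "Patients with two or more CEC-classified SAE will be counted only once".
- **Serious procedure-related AE rate (SAP 7.8.1).** The numerator is the "total number of patients with CEC-classified SPRAE from the time of implant procedure", over the same denominator.
- **Device-related AE rate (SAP 7.8.2).** This is also built on CEC-classified events.
- **Deaths (SAP 7.12).** "Only CEC classification of Deaths will be used for analysis".
- **Interim (SAP 7.13).** "An interim analysis once 15 patients have been enrolled and/or implanted will be performed". No data-cut, adjudication or follow-up condition is given.
- **Pending events (Protocol 6.3).** Reports show the CEC classification once it is final. "In interim reports, pending events will be listed with the investigator classification". Meetings follow event numbers or trial milestones, but take place "no less than twice a year while the study is ongoing". An event for which the committee wants more source documents stays pending.
- **Declared changes (SAP 7.14).** Only the urine-output timepoint is listed.

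**The concern.** The protocol provides a fallback for events that the committee has not yet ruled on. The SAP's rate definitions do not carry it over. A numerator defined by CEC-classified events will be programmed that way, and a patient whose only SAE is pending then stays in the denominator and drops out of the numerator. The trigger adds a second route to the same error: a patient implanted shortly before the cut counts as event-free after only a few days of observation.

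Both errors push the rate down. Protocol section 7 allows an interim report for regulatory or publication purposes. Protocol 5.2 describes this as the first human use beyond 90 minutes of treatment. An understated safety rate could therefore be the first one seen outside the study. Two analysts could also produce different interim rates from the same data, one reading the SAP alone and the other reading the protocol's fallback into it.

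**Working it through.** The documents state no interim safety rate, so there is no planned figure to reproduce. The check sets out the rules, then sizes the effect under stated assumptions.

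**1. How each type of patient is scored at the interim**

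| Patient at the cut | SAP 7.8.1, read literally | With the Protocol 6.3 classification carried into the rate |
|---|---|---|
| At least one adjudicated SAE | Counted | Counted |
| Only pending SAEs | Event-free | Counted under the investigator classification, flagged |
| No SAE yet, 30-day window open | Event-free | Event-free (Protocol 6.3 does not address this) |

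The second row is the adjudication effect. The third needs a separate fix.

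**2. Effect of pending events, taking 15 As-Treated patients**

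Shift = k/15, where k is the number of patients whose only SAEs are pending. One patient: 1/15 = 6.7 percentage points. The documents give neither k nor the SAE rate, so the counts below are assumed. Intervals are exact (Clopper-Pearson) 95%.

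| Patients with any SAE | Pending only (k) | CEC-only rate | Rate including pending |
|---|---|---|---|
| 3 | 3 | 0/15 = 0% (0 to 21.8) | 3/15 = 20.0% (4.3 to 48.1) |
| 6 | 0 | 6/15 = 40.0% (16.3 to 67.7) | 6/15 = 40.0% (16.3 to 67.7) |
| 6 | 2 | 4/15 = 26.7% (7.8 to 55.1) | 6/15 = 40.0% (16.3 to 67.7) |
| 9 | 1 | 8/15 = 53.3% (26.6 to 78.7) | 9/15 = 60.0% (32.3 to 83.7) |

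**3. Is a backlog plausible?**

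Inputs: 30 implants (SAP 2.3), 12 to 24 months of enrolment (Protocol 3.5), and a gap of about six months if the CEC meets only at its minimum frequency, evenly spaced. Implants per gap: 30/12 × 6 = 15, and 30/24 × 6 = 7.5. A minimum-frequency gap could thus span half to all of a 15-implant interim. This is an upper end, because meetings may also be timed to milestones.

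**4. Open 30-day windows**

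With even accrual, 30/24 = 1.25 to 30/12 = 2.5 patients are implanted per month. Roughly 1 to 3 patients would have been implanted in the last 30 days before any cut.

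**5. What the trigger allows**

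The SAP expects about 50% of enrolled patients not to receive the pump. Fifteen enrolled then gives 15 × 0.50 = 7.5 implants, against 15 if the trigger is implants. With 7 or 8 patients, one pending-only patient moves the rate by 1/7 = 14.3 or 1/8 = 12.5 points.

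Timing: 60 enrolled over 12 to 24 months is 5 to 2.5 per month, so 15 enrolled takes 3 to 6 months. At 2.5 to 1.25 implants per month, 15 implants takes 6 to 12 months. The two readings differ by 3 to 6 months.

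**The case against.** Several points on the other side stand.

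- A reader might infer that the protocol requires pending events to count in the primary rate and that the SAP sets the opposite rule. The documents do not go that far. Protocol 6.3 speaks of listing, and the SAP has no rule that excludes pending events; it is silent. SAP section 1 says it is to be read together with the protocol, so the fallback could be read in. That is harder for deaths, where SAP 7.12 admits only the CEC classification.
- A reader might infer that unadjudicated SAEs and deaths disappear. They do not. SAP 7.9.1 adds an overall summary and listing by investigator classification (Table 14.3.1.1.2 and Listing 16.2.7.2). SAP 7.12 still calls for the number of deaths, vignettes and a listing; its restriction concerns how deaths are classified. However, the investigator table uses the ITT population, while the primary safety table is As-Treated, and no planned output combines final CEC with pending investigator classifications.
- A reader might take the backlog in step 3 to mean that a 40% rate would be reported as 20% or 0%. That needs an assumed rate, the minimum meeting schedule, the worst timing, and no affected patient with another adjudicated SAE. Protocol 5.3 promises timely adjudication, and a planned interim is a natural milestone, although nothing ties a CEC meeting to it.
- The investigator classification is provisional, and the CEC may later change it. That is a reason to show both rates. It does not justify scoring a pending event as no event.
- The interim is descriptive, with no stopping boundary. The enrolment pause in Protocol section 6 and the SAE reporting times in 6.1 do not depend on this rate. The final analysis is protected, because the last CEC meeting follows completed follow-up and receipt of all adverse event forms.

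**Conclusion.** The point holds for the interim primary safety rates, and for the device-related AE rate in SAP 7.8.2. Read literally, the SAP scores a patient with only pending events as event-free. It does the same for a patient with an open 30-day window and no event yet. SAP 7.14 does not declare the departure from Protocol 6.3. Leaving pending events out can lower the rate but cannot raise it.

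The adjudication effect is 6.7 points per pending-only patient at 15 As-Treated patients, and zero if nothing is pending. The example of 26.7% against 40.0% rests on assumed counts. The follow-up effect concerns roughly 1 to 3 patients under even accrual, and remains even if adjudication is fully current. The matter should be settled before the interim. It does not touch the final analysis or the enrolment-pause rule.

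**What to change.** 1. **Pending events.** In SAP 7.8.1, 7.8.2, 7.9.1 and 7.12, state that at an interim analysis, events and deaths awaiting CEC adjudication are included under the investigator classification and flagged as pending, consistent with Protocol 6.3. Show the CEC-only rate beside it.
2. **Trigger and follow-up.** In SAP 7.13, state one trigger in As-Treated patients. Compute the interim primary safety rates only in As-Treated patients whose 30-day window has closed by the data cut, including those in that group who died or exited early. Set eligibility by calendar time, so that a recent patient is not brought in because of an early death. State the anchor: SAP 7.8.1 words the window as post-implant, while Protocol 4.8 places the visit 30 days after retrieval. Report events in later patients separately.

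The cost is SAP wording and one extra line per rate. The interim rate may look less favourable. It will also either rest on fewer patients or come later: by weeks if the trigger is 15 implants, and by about 3 to 6 months more if it was meant as 15 enrolled. A CEC meeting before the cut would shrink the pending group, but does not replace the rule.

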4.8 Follow-Up

Patients with the pump implanted will be followed for adverse events for 30 days (± 7 days) post device retrieval. If implanted patients are still hospitalized at 30 days due to an adverse event relating to the device or any study related procedures, they must be followed until resolution of the adverse event, resolution with sequelae, or until a terminal event. Protocol required data collection for patients with the pump implanted will be for 30 days post device retrieval (± 7 days) per **Appendix A**.

The following data will be collected:

- NYHA classification
- Cardiovascular exam (edema, pulmonary auscultation, weight),
- Vital signs (HR, BP, RR)
- Dyspnea evaluation
- KCCQ, EQ5D
- Document current cardiovascular/renal medications and adverse events
- Blood and urine labs per **Appendix A**

Patients that have an attempted implant but do not have the pump implanted will be followed for adverse events for 30 days (± 7 days) post attempted implant. If attempted implant patients are still hospitalized at 30 days due to an adverse event relating to the device or any study related procedures, they must be followed until resolution of the adverse event, resolution with sequelae, or until a terminal event.

Terminal events are death, LVAD implantation, heart and/or kidney transplantation, dialysis, ultrafiltration or CRRT.

Patients who are enrolled and undergo anatomy screening and/or invasive hemodynamic measurements who do not have an attempted implant will be followed for adverse events for 7 days (\pm 2 days) post anatomic screening or invasive hemodynamics (whichever is later) or until hospital discharge, whichever is first.

Every attempt should be made to perform follow-up visits in person. Should extenuating circumstances (e.g., COVID-19 global pandemic travel restrictions) impact a site's ability to perform follow-up visits in person, notify the sponsor and make every attempt to collect the protocol required data via other means (e.g., telephone, video conference, blood and urine labs at a non-hospital lab).

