Appendix A: Schedule of Visits and Procedures

Category	Pre-Therapy		Aortix Therapy								Post-Therapy			
	Pre-Implant Period (Baseline Monitoring)	Day of Implant (Pre-implant)	Implant to Pump Retrieval					Once Congestion Target is Met and Within 12 hours of Beginning Weaning ^α	Day of Pump Retrieval (Pre-Pump Retrieval)	Cath-Lab Pre-Pump Retrieval	Post-Pump Retrieval Monitoring		Follow-Up: 30 days (± 7 days) from Pump retrieval	
	Current hospitalization once	once	Once (after pump deployed)	2 hours post implant ⊕ (± 30 min)	6 hours post implant (± 30 min) and Every 6 hours (± 1 hour) for 24 hours post implant	Every 24 h (± 2 hours)◆	Pump Speed Changes #	once	once	once	Every 24 h (± 2 hours)	Once at 72 hours post retrieval (± 4 hours) or discharge (whichever is earlier)	once	
Informed Consent ¹	X													
Med History	X													
NYHA Class	X											X	X	
Cardiovascular exam (edema, pulm auscultation, weight)	X	X				X		X				X	X	
Vital Signs: HR, BP, RR #	X	X		X	X	X	X	X		X		X	X	
Height	X													
Fluid Ins and Outs*		X*		X	X	X	X	X		X	X ^β			
Dyspnea Evaluation		X				X		X				X	X	
KCCQ, EQ5D	X												X	
HEMODYNAMICS														
CVP, PAP #		X		X	X	X	X	X		X				
PCWP #		X		X		X	X	X		X				
SvO ₂ , SaO ₂ **		X		X	X	X		X		X				
IMAGING														
Anatomy Screening	X													
Echo	X							X						
Fluoro Image			X							X				
MEDICATIONS	X		Record all cardiovascular/renal medications and medication changes.****										X	
OTHER EVENTS***			Record all adverse events, readmissions and mortality.											

1 Patient must sign informed consent before undergoing PA catheter placement for verification of inclusion criteria for objective measure of congestion or before undergoing imaging to assess anatomy for exclusion criteria for contraindicated anatomy.

α One time assessments to be taken once congestion targets are met or therapy has been deemed ineffective (decision has been made to retrieve device). These assessments should be performed before the pump speed is turned down; within 12 hours of beginning weaning.

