5 STUDY ENDPOINTS

5.1 Primary Safety Endpoints

- Rate of Occurrence of Serious Adverse Events (rate will be calculated and reported) [timeframe: enrollment to 30 day visit];
- Rate of Occurrence of Serious Procedure Related Adverse Events (rate will be calculated and reported) [timeframe: procedure to 30 day visit].

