5.2 Device Performance Endpoints

- Deployment and retrieval procedures success rates (rates will be calculated and reported);
- Rate of occurrence of ADS, ARS and pump device-related adverse events (includes device malfunctions) (rate will be calculated and reported) [timeframe: implant attempt/implant to 30 day visit].

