7.8.2 Device Performance

A Device Performance analysis will be performed for ITT or As-Treated population to include:

- Deployment success defined as total number of patients with a successfully implanted Aortix Pump compared to the total number of patients within ITT population.
- Retrieval success defined as total number of patients with a successfully retrieved Aortix Pump compared to the total number of patients within the As-Treated population.
- Percentage of patients with ADS, ARS and pump device-related adverse events defined as the total number of patients with CEC-classified AEs of the corresponding category from the time of implant procedure through 30 days post-implant Follow-Up compared to the total number of patients in either the ITT population or As-Treated population as appropriate.

Descriptive summary will be provided for variables within Device Performance analysis. Corresponding listing will be provided for ITT population.

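### SAP 7.8.1 and 7.8.2 count the 30-day safety window from implant, while the protocol's 30-day visit for implanted patients is counted from pump retrieval

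*SAP*

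**What the plan says.** **Operative definitions (SAP 7.8).** The first primary safety bullet in 7.8.1 counts patients with a serious adverse event, as classified by the clinical events committee, "from the time of enrollment through 30 days post-implant Follow-Up". The second bullet counts serious procedure-related events "from the time of implant procedure through 30 days post-implant Follow-Up". In 7.8.2 the device-related adverse event bullet runs "from the time of implant procedure through 30 days post-implant Follow-Up compared to the total number of patients in either the ITT population" or the As-Treated population, as appropriate.

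**Endpoint definitions (SAP 5.1 and 5.2).** The procedure-related endpoint is worded "Rate of Occurrence of Serious Procedure Related Adverse Events (rate will be calculated and reported) [timeframe: procedure to 30 day visit". The device-related endpoint carries "timeframe: implant attempt/implant to 30 day visit". The serious adverse event endpoint also ends at the 30-day visit. Protocol 3.3.1 and 3.3.2 give the same time frames.

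**When that visit takes place (protocol).** Section 4.8 states: "Patients with the pump implanted will be followed for adverse events for 30 days (± 7 days) post device retrieval". The Appendix A column is headed "Follow-Up: 30 days (± 7 days) from Pump retrieval". The only follow-up counted from implant is for patients in whom an implant was attempted but failed, who "will be followed for adverse events for 30 days (± 7 days) post attempted implant".

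**Declared changes.** SAP 7.14 lists departures from the protocol's analyses. The only one listed concerns the urine-output time point.

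**The concern.** The section that a programmer works from gives a different anchor from the section that defines the endpoint. Follow-Up is also the SAP's name for the scheduled visit (for example in 7.9.2). The phrase can therefore mean a cut on day 30 after implant, or the visit itself. Nothing in 7.8 settles which.

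Primary safety is analysed in the As-Treated population, which contains only patients with the pump implanted. The protocol counts follow-up from retrieval for every one of them, so the stated anchor fits nobody in that analysis. In 7.8.2 it fits only patients with a failed attempt.

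Under the literal reading, a patient whose first qualifying event falls after day 30 from implant but before the visit drops out of the headline percentage. The time removed is at the end of post-retrieval observation, and 7.8.1 expressly counts retrieval complications as procedure-related.

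**Working it through.** The plan gives no figure to reproduce here: the sample size was not statistically derived, and no test or performance goal is attached to these rates. The check is arithmetic on the windows.

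**Inputs**
- d = days from implant to retrieval. Assumed range 2 to 7. The lower end is the minimum initial running time in protocol 4.5.2.1, and the upper end is the tested duration in protocol 4.5. Neither is a hard limit, and protocol 5.3 allows retrieval at any time if therapy is judged ineffective or unsafe.
- v = days from retrieval to the visit: 23, 30 or 37, from the 30 (±7) day window in protocol 4.8 and Appendix A.
- Literal cut in SAP 7.8 = day 30 after implant.
- Implanted patients: 30 (SAP 2.3).

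**Formulas**
- Literal cut, in days after retrieval = 30 − d
- Days lost = max(0, v − (30 − d))
- Share of the nominal 30 post-retrieval days lost = d / 30

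| d | Cut, days after retrieval | Lost, v = 23 | Lost, v = 30 | Lost, v = 37 | Share of nominal 30 days lost |
|---|---|---|---|---|---|
| 2 | 28 | 0 (cut is 5 days after visit) | 2 | 9 | 2/30 = 6.7% |
| 4 | 26 | 0 (3 days after) | 4 | 11 | 4/30 = 13.3% |
| 5 | 25 | 0 (2 days after) | 5 | 12 | 5/30 = 16.7% |
| 7 | 23 | 0 (same day) | 7 | 14 | 7/30 = 23.3% |

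The effect of the anchor alone is the v = 30 column, 2 to 7 days. The v = 37 column adds 7 days that come from the visit window, because a fixed cut is being compared with a late visit.

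**Weight of one patient**
- As-Treated, 30 patients: 1/30 = 3.3 percentage points.
- ITT denominator in 7.8.2: between 1/30 = 3.3 and 1/60 = 1.7 points. Sixty is the enrolment cap. It would be reached only if every enrolled patient had an implant attempt, so the true weight should lie nearer 3.3.
- Interim analysis (SAP 7.13), if 15 implanted patients are analysed: 1/15 = 6.7 points.

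The documents give no event times, so the number of patients affected cannot be calculated.

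**The case against.** The best defence is that this is loose wording. Follow-Up is capitalised and is the visit's name, and Appendix A schedules only one such visit for implanted patients. SAP section 5 says the 30-day visit, and the SAP asks to be read with the protocol. The silence of 7.14 fits equally well with no change being intended. That reading is plausible and may be what the authors meant. Even so, the text then attaches the wrong anchor to the visit, and two programmers could use different cut-offs and each cite the SAP.

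The second argument is that little hangs on it. This is a feasibility study with descriptive rates, and each patient's data are reviewed individually. Adverse events are collected until study exit. They are listed for all enrolled patients and tabulated for the ITT population, with no 30-day cut stated. This stands in part: no event disappears from the report, and the As-Treated rate could be recomputed from the listings under either window. However, the ITT tables do not replace the As-Treated headline percentages. A gap between the two could come from the population or from the window, and a reader of the tables could not tell which.

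The third is that a fixed post-implant window might be deliberate. If so, it changes the primary safety endpoints and belongs in SAP 7.14, where it does not appear.

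**Conclusion.** The concern holds and should be fixed. As written, SAP 7.8.1 (both bullets) and 7.8.2 (third bullet) state an end point that does not match SAP 5.1 and 5.2 once the protocol's timing of the visit is applied. SAP section 5 does not itself name an anchor, so the conflict runs through protocol 4.8 and Appendix A.

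The wording mismatch is certain; its effect on the reported rates is not. With 2 to 7 days of support assumed, the literal reading removes 2 to 7 nominal post-retrieval days, and from 0 to 14 across the visit window. Each patient missed costs 3.3 points with 30 implanted. If the phrase is applied as the visit, or if no first event falls in the gap, the rates do not change.

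**What to change.** In SAP 7.8.1 (both bullets) and 7.8.2 (third bullet), change the end of the window as follows:
- Implanted patients: *through the 30-day Follow-Up visit (30 ±7 days after pump retrieval), or study exit if earlier*.
- ITT patients without an implant (7.8.2 only): *through 30 (±7) days after the attempted implant*.

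This brings 7.8 into line with SAP section 5 and protocol 4.8. Protocol 4.8 extends follow-up for patients still in hospital at 30 days because of a device- or procedure-related event. One added sentence should say whether later events in those patients enter the rates or appear only in the listings. If the sponsor does want a fixed window from implant, 7.14 should declare it as a change, with a reason.

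The cost is SAP wording only, with no new data. The rates may become slightly less favourable, although a rise is not guaranteed because the literal cut runs up to 5 days past an early visit in the range examined. Post-retrieval observation will vary between patients from 23 to 37 days, which the tables should footnote.
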